We recently reported the first prospective assessment of QSM during longitudinal follow-up of human CCM subjects, and correlated paired QSM assessments during 1-year epochs with new clinical events (58). Among cases without recent bleeding or lesion growth within a year of the first measurement, CCM lesions that remained stable during longitudinal follow-up had a tiny average decrease (-3.2%) in mean lesional QSM. CCMs with demonstrated growth or symptomatic bleeding exhibited a significant increase (+44%) in mean lesional QSM (Figure 6). Receiver operating curves (ROC) of QSM change in individual subjects demonstrated a sensitivity of 82.29% and specificity of 88.89% at a +5.81% threshold change, highly significant ( $p = 0.0004$ ), with a mere **+5.81% QSM change. These results link a robust QSM change directly to clinical events, and define a threshold QSM change as a sensitive and specific biomarker event.**

**QSM change and clinical events in CAs after recent Symptomatic Hemorrhage.** In further pilot studies, we assessed lesional QSM change during prospective **follow-up of a pilot cohort of CA patients with a clinical bleed within the prior year (meeting the proposed trial criteria)** (59).

Sixteen subjects followed for 1 or 2 years (total 22 person-year epochs), underwent paired QSM assessments at the beginning and end of each person-year epoch. Mean QSM in the index CA hemorrhagic lesion increased by an average of +7.93% per person-

[figure not shown]

year epoch in the full cohort. Closer examination revealed 10/22 epochs with a documented threshold biomarker event ( $\geq 6\%$  QSM increase). This was twice as frequent as clinical events. No clinical event occurred without a threshold increase in QSM (Figure 7). A primary aim of the proposed trial shall explore whether the change in QSM is altered by statin treatment. A secondary aim shall explore the relationship of QSM change to clinical events in statin and placebo treated subjects.

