## **6.4 ROCK Activity Assays**

### **6.4.1 ROCK Activity on Peripheral Leukocytes**

Our collaborator [name] has shown that ROCK activity may be quantified in human leukocytes isolated from peripheral blood [by assessing the ratio of pMBS/glycer-aldehyde-3-phosphate dehydrogenase (GAPDH) protein], and that this activity is inhibited by statins (54, 86, 87). It is our intention to investigate whether ROCK activity in peripheral blood leukocytes is impacted by the treatment intervention at the proposed doses in CA subjects with recent hemorrhage. We have already performed these analyses in correlation with brain permeability measurements and disease severity in CAs, in conjunction with prior exploratory developmental project (R21NS087328), and data from those studies has been published (88).

In addition clinical laboratory tests to be performed at baseline, and at 12 and 24 months follow-up visits (V1, V3 and V4), 5-10 ml of blood are collected into heparinized vacutainer tubes. Leukocytes are isolated from the blood and frozen at -86°C after fixing in 50% trichloroacetic acid/50 mM dithiothreitol. Cells are thawed and relative ROCK activity in leukocytes is assessed by Western transfers as described by our collaborator [name] (54, 86, 87, 89). Since ROCK phosphorylates MBS (MYPT1), relative ROCK activity will be assessed by the ratio of the intensity of pMBS staining/GAPDH staining. GAPDH is chosen as reference since it was shown to be a more reliable internal control in Western blot analysis of leukocytes than other housekeeping proteins (90). For these quantitative assays, we shall use the pMBS antibody developed by our collaborator [name], targeting the Thr of MBS site, known to be specific for only ROCK and not other serine/threonine kinases (91, 92). Lysophosphatidic acid-stimulated NIH3T3 fibroblast lysates will be run on all gels as a positive control to standardize results between experiments (89). We shall enter the pMBS/GAPDH ratio in immunoblots for each subject/visit as "ROCK Activity on Peripheral Leukocytes" for subsequent secondary analyses as proposed in the SAP, comparing placebo and intervention groups at baseline, and at 1 and 2 year follow-up.

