## 9.3 Sample Size and Accrual

### 9.3.1 Sample size and Treatment Effect Estimation

Sample size calculations were based on providing sufficient power to test the primary hypothesis, that the proposed intervention impacts QSM biomarker activity (indicative of reduced or increased lesional bleeding) during 2 years of prospective follow-up after a recent CA SH. **The primary outcome is the mean % change in lesional QSM per year (called the change score).** Each patient contributes two outcome measurements (at year 1 and year 2, i.e. epochs). Evaluation of the intervention on this outcome will be performed as a time-averaged difference between two arms using a repeated measures analysis implemented as a linear mixed model and intention-to-treat principle (110).

**Estimating a “First-in-Man” treatment effect on a biomarker** can be difficult when such effect is demonstrated mechanistically but the translation to a human effect size remains unknown (111). Based on pilot data linking QSM change to clinical events, **we propose a minimum, clinically meaningful and mechanistically plausible treatment effect to be a 20% absolute difference in the mean change score.** It would be “a minimum expected effect”, <1/2 the mean 44% QSM increase observed with CA bleed or growth during longitudinal 1-year follow-up of previously stable lesions; and “clinically meaningful”, > 3X the threshold of QSM change associated with maximum sensitivity-specificity on ROC analyses (58). The absolute QSM effect size postulated herein is “plausible mechanistically”. It would be 0.0068 ppm [20% of 0.0340 ppm mean QSM change observed during follow-up of CA with SH (59)], 6-22 folds lower than the observed range of atorvastatin treatment effect on Perls stain intensity in *Ccm1* and *Ccm3* murine models (Figures 2, 3, 5).

One-year %QSM change in 16 pilot study patients (Figure 7), followed for either 1 or 2 years (22 patient-year epochs), was used to estimate the 1-year/patient standard deviation and within-patient correlation of the primary outcome in trial candidates. A sample size calculation was performed using a repeated measures analysis of two annual percent QSM change scores, assuming a two-tailed test, power = 0.9 and alpha = 0.05 (112). The actual within person correction from the pilot data was estimated at approximately -0.6 (Spearman); however, as this was based on only 6 patients with two-year’s

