To address **secondary aims**, each of the other outcomes will be analyzed with a similar approach, first per intention-to-treat sample in patients receiving two annual epochs of follow-up, and second by treatment-rendered in all patients with at least one annual epoch of measurements. To assess the difference in level of DCEQP permeability in lesion and brain between the two arms, a linear mixed model adjusted for gender as described for QSM will be used to evaluate the difference in percent change per year in lesional and WMF permeability. A similar adjusted linear logistic mixed model for the binary outcomes will be used to evaluate the difference between the two arms in the rates of symptomatic hemorrhage (per adjudicated definition), lesion expansion, and “biomarker event” (increase in QSM during an epoch above the pre-defined 6% threshold). To assess the difference of event rates for adverse events (AEs) per patient, an adjusted Poisson linear mixed model controlling for gender will be used to regress count outcomes in order to evaluate the difference in AE event rates between the two treatment arms. The AEs will be assigned preferred terms per body systems according to the Medical Dictionary for Drug Regulatory Affairs (MEDDRA) classification of the WHO terminology. AEs (categorized by body system) and abnormal laboratory data will be summarized and compared by treatment group. The compliance rate, general attrition rate and the attrition rate due to adverse events between the two groups shall also be compared. For analysis of leukocyte ROCK activity and functional outcomes (mRS, Euro QOL 5D and VAS, Neuro QOL Communication, and mini-MS score), an adjusted linear mixed model will be used to evaluate the difference in respective outcome score change per year between the two arms. We will report point-estimates, confidence intervals, and p-values for each analysis.

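### Section 9.5 analyses leukocyte ROCK activity as change per year, at odds with the by-visit comparison in Section 6.4.1; a baseline-adjusted comparison of levels at 12 and 24 months would use the same samples better

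*Combined protocol and SAP*

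**What the plan says.** Section 9.5 handles the secondary outcomes by an approach similar to that for QSM. They are analysed "first per intention-to-treat sample in patients receiving two annual epochs of follow-up". A further analysis, by treatment received, takes in everyone who has one or more annual epochs. For leukocyte ROCK activity, in a sentence shared with the functional outcomes, "an adjusted linear mixed model will be used to evaluate the difference in respective outcome score change per year between the two arms". For permeability the stated purpose is "To assess the difference in level of DCEQP permeability in lesion and brain between the two arms", but the model "will be used to evaluate the difference in percent change per year in lesional and WMF permeability".

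Section 9.5 does not define change per year for these outcomes. The nearest definition is the one for QSM. Section 9.3.1 says "Each patient contributes two outcome measurements (at year 1 and year 2, i.e. epochs" and analyses the two values as a time-averaged difference. In the pilot cohort described in Section 2.2, subjects "underwent paired QSM assessments at the beginning and end of each person-year epoch", so the second-year change is month 24 minus month 12.

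Section 6.4.1 describes the ROCK analysis differently, as "comparing placebo and intervention groups at baseline, and at 1 and 2 year follow-up", and refers to the SAP for it. Section 9.5 contains no such by-visit comparison. Section 9.2 lists the ROCK ratio for each subject and visit, but lists changes in permeability for both lesion and white matter.

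**The concern.** An annual rate suits lesional iron, which builds up. Section 6.4.1 treats leukocyte ROCK activity as something that statins inhibit, so the natural question is how far it is lowered at each on-treatment visit. White-matter permeability may behave in the same way. Section 2.2 reports it as lower in statin users than in non-users, but this is a retrospective comparison of 9 with 60 patients and a trend only (P=0.07, Figure 8 legend).

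The stakes are interpretive. Leukocyte ROCK is the only measure of target engagement planned for all subjects. If QSM shows no effect, the ROCK result helps to tell a dose that missed its target from a mechanism that does not work. An analysis that drops one of the two on-treatment samples, and reports a number easily misread as the size of the inhibition, weakens that distinction.

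**Working it through.** **The plan's own figure.** For QSM, with SD 30, difference 20, two epochs, correlation 0, two-sided alpha 0.05 and power 0.90 (Sections 9.3.1 and 9.5): n = 2 × 30² × [(1 + 0)/2] × (1.960 + 1.282)² / 20² = 23.64 per arm. That gives 24 by the normal approximation and 25 by the t distribution, matching the stated 25. Then 25/(1 − 0.375) = 40. The figure reproduces with two annual change scores per patient. The plan gives no power for ROCK or white-matter permeability.

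**What change per year estimates.** Let Y0, Y12 and Y24 be the levels, and let the drug shift the level by D at month 12 and hold it there.

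- Epoch changes averaged: [(Y12 − Y0) + (Y24 − Y12)]/2 = (Y24 − Y0)/2. The expected difference is D/2 and Y12 has weight 0.
- Slope through 0, 1 and 2 years: weights (−0.5, 0, 0.5), the same result.
- Change from baseline divided by elapsed years, averaged: [(Y12 − Y0) + (Y24 − Y0)/2]/2, weights (−0.75, 0.50, 0.25). The expected difference is 0.75 D and Y12 counts.

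In simulated data with a true D of −1, the epoch mixed model, the slope mixed model and (Y24 − Y0)/2 all gave −0.4728. Adding noise to month 12 and +5 to the treated arm's 12-month values left the epoch estimate at −0.4728.

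**Limits of the cancellation.** It is exact for absolute change in patients with both epochs, which is the stated intention-to-treat set. For percent change re-based each year it is approximate, because Y12 stays in the denominators. With an assumed coefficient of variation of about 20%, a sustained fall of 20% or 30% gives −10.2% or −15.3% per year. It does not hold for a patient with only the first epoch in the treatment-rendered analysis, who contributes Y12 − Y0.

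**Precision.** Assume equal variance at each visit (SD² = 1) and a common between-visit correlation r. The documents give neither. Variances are put on the scale of D:

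- as written (epoch or slope): Var(Y24 − Y0) = 2(1 − r)
- both visits, change from baseline: Var[(Y12 + Y24)/2 − Y0] = 1.5(1 − r)
- both visits, baseline as covariate: (1 + r)/2 − r²

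| r | As written | Both visits, change | Both visits, adjusted | Ratio, month 12 alone | Ratio, combined |
|---|---|---|---|---|---|
| 0.3 | 1.40 | 1.05 | 0.56 | 1.33 | 2.5 |
| 0.5 | 1.00 | 0.75 | 0.50 | 1.33 | 2.0 |
| 0.7 | 0.60 | 0.45 | 0.36 | 1.33 | 1.67 |

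Power with 25 per arm, an assumed shift of 0.6 SD and two-sided alpha 0.05 (noncentral t):

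| r | As written | Change from baseline ÷ years | Both visits, change | Both visits, adjusted |
|---|---|---|---|---|
| 0.3 | 0.42 | 0.51 | 0.53 | 0.79 |
| 0.5 | 0.55 | 0.65 | 0.67 | 0.84 |
| 0.7 | 0.77 | 0.86 | 0.87 | 0.93 |

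**The case against.** Several counter-arguments stand.

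- **Units.** The standard error of (Y24 − Y0)/2 is also half that of Y24 − Y0, so the test and p-value do not change. A reader might infer that halving the estimate could itself hide target engagement. It cannot: doubling the per-year figure recovers the two-year change.
- **Ambiguity.** Because change per year is undefined, a reader might infer that month 12 is always ignored. On the reading that divides change from baseline by elapsed years, it carries more weight than month 24.
- **Two effects in one ratio.** The 2.5, 2.0 and 1.67 combine use of month 12 with baseline adjustment. Like for like, month 12 is worth 1.33. The split depends on order: with baseline adjustment made first, month 12 is worth more.
- **Sample size used.** The 25 per arm is the number left after the plan's allowance for losses. With all 40 per arm, power as written would be 0.61, 0.76 and 0.93.
- **By-visit comparison.** Section 6.4.1 already states it, so the level comparison is not absent from the plan. Section 9.5 fails to carry it through.

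Three further inferences are not supported. Leukocyte ROCK is not the only direct evidence on the target, because Section 6.4.2 plans assays on any excised lesions, though only in patients who come to resection. The one-month mouse result in Section 2.2 concerns lesional iron leak and says nothing about how fast leukocyte ROCK or white-matter permeability responds. Lesional permeability should not be moved to a level analysis on this argument: Section 2.2 reports it as change within lesions that bled and found no difference in level with statin use.

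**Conclusion.** The point holds for leukocyte ROCK activity and, with weaker support, for white-matter permeability. Sections 6.4.1 and 9.5 disagree on ROCK, Section 9.5 is inconsistent within itself on permeability, and change per year is undefined for both. Those inconsistencies need no assumption.

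On the plan's epoch definition, or as a slope, the intention-to-treat ROCK estimate is D/2 per year for a sustained shift and does not use the 12-month sample. The cost is precision, not bias in the test. In the case worked above, power rises from 0.42–0.77 to 0.53–0.87 by using both visits, and to 0.79–0.93 with baseline adjustment as well. SD, r, the 0.6 SD shift and an effect fully present by month 12 are assumptions. The level analysis with baseline adjustment had the highest power on every reading computed. The primary QSM analysis and its sample size are not affected.

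**What to change.** In Section 9.5, analyse leukocyte ROCK activity as the between-arm difference in level at months 12 and 24. Use a repeated-measures mixed model with baseline value, sex, visit and arm-by-visit terms, and report each visit and the average of the two. Apply the same model to white-matter permeability. Adjusting for baseline still addresses change from baseline, so it fits the Section 9.2 listing. Align Section 6.4.1 with the new wording, and keep QSM and lesional permeability as change measures, with change per year defined for each outcome that retains it.

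The cost is SAP text only. Samples, scans, visits and sample size stay as they are.

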## Imputation of Missing Outcomes Data, and Sensitivity Analyses

As mentioned above, every effort will be made to minimize the number of patients will missing outcome measures. However, despite these best efforts, it is likely that some missing outcome data will be present in this data set. In order to account for these missing outcome values, we will perform a sensitivity analyses that uses a Markov chain Monte Carlo (MCMC) model to impute several possible measures for patients missing the primary outcome.

With multiple imputation (MI), we assume that the missing data points are missing at random (MAR) (119). We will use those baseline demographic variables, which are strongly associated with clinical outcome, to improve the missing outcome imputations. We will then generate an iteration series plot and autocorrelation function (ACF) plot for MCMC simulation. We shall plan 20 imputations with a 98% relative efficiency to accommodate a worst-case scenario, where 37.5% of the outcomes data points are missing (120). To verify if the missing data points occur at random we will utilize a tipping-point approach (121) that will follow MI procedure for sensitivity analysis and estimation of the MI departure from the MAR assumption. We shall use the sensitivity analysis to recalculate efficacy estimates from regression models described in the data analysis of the primary and secondary outcomes. This will help determine how sensitive efficacy estimates are under different assumed distributions for missing outcomes data. In other words, the results obtained by imputing missing data with several plausible outcomes will give a range of possible treatment effects under different assumptions of missingness.

We will have greater confidence in efficacy estimates if we obtain clinically and statistically significant results under the worst-case scenarios from the sensitivity analyses (e.g. imputing no improvement in the QSM change scores for all patients with missing data in the active treatment arm). In contrast, greater caution should be given to estimates of efficacy if results obtained from regression analyses are no longer clinically and statistically significant under extreme scenarios for the missing data. SAS 9.4 (SAS Institute Inc., Cary, NC, USA) will be used for MI and sensitivity analysis.

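### The named worst-case imputation, read as 0% QSM change, is milder than the pilot's untreated course, so surviving it would overstate robustness

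*Combined protocol and SAP*

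**What the plan says.** The subsection on imputation and sensitivity analyses at the end of Section 9.5 plans multiple imputation under MAR, with 20 imputations and a ceiling of 37.5% missing outcomes. It says efficacy estimates will earn greater confidence if they stay clinically and statistically significant under worst-case scenarios. The one example is "imputing no improvement in the QSM change scores for all patients with missing data in the active treatment arm". No numeric value is given, and nothing is said about missing placebo patients in that scenario.

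The same subsection introduces a second tool: "To verify if the missing data points occur at random we will utilize a tipping-point approach". The sentence goes on to mention sensitivity analysis and estimating departure from MAR, but no range of shifts is stated.

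Section 2.2 supplies the yardsticks. In the pilot cohort that met the trial's criteria, mean QSM in the index lesion "increased by an average of +7.93% per person"-year epoch. Among lesions with no recent bleeding or growth at the first measurement, "CCMs with demonstrated growth or symptomatic bleeding exhibited a significant increase (+44%) in mean lesional QSM", while those that stayed stable "had a tiny average decrease (-3.2%) in mean lesional QSM".

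**The concern.** A rise in QSM is the bad direction, since it indicates lesional bleeding. A change score of 0% therefore lies close to what stable lesions showed (-3.2%), below the untreated pilot mean (+7.93%), and a long way below lesions that bled or grew (+44%). Giving 0% to every missing active-arm patient assigns them a fairly good course under a worst-case label.

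The label matters because of where the check sits. Sections 9.2 and 9.5 restrict the initial intention-to-treat analysis to patients measured in both periods, so the sensitivity analyses are the main protection against informative missingness. Missingness may also be related to bleeding. Section 9.3.2 expects 20-30% of patients to reach the symptomatic-hemorrhage endpoint, and Section 7.3.1 says a lesion that has bled will be considered for treatment. My inference is that a resected lesion could not give a comparable follow-up QSM value.

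At stake is whether a positive result is reported as robust to the worst case when it has met only a moderate test.

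**Working it through.** **Inputs.** Section 9.3.1: design effect 20 points, SD 30, within-person correlation 0, two annual change scores, "assuming a two-tailed test, power = 0.9 and alpha = 0.05". Section 9.5: up to 37.5% missing, 20 imputations. Section 2.2: +7.93% per epoch (16 patients, 22 epochs) and +44%. Assumptions: placebo mean P equals the pilot mean, and patients with missing data lack both epochs.

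**1. The plan's own figures.** The SD of a patient's two-epoch mean is 30 × √((1+0)/2) = 21.2. A noncentral-t calculation gives 25, 44 and 17 per arm for 20, 15 and 25 points, as stated. Inflation: 25/(1 − 0.375) = 40. Relative efficiency: 1/(1 + 0.375/20) = 0.982. All are reproduced.

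**2. How mild 0% is.** It lies 7.93 points below the pilot mean, and 7.93/20 = 40% of the design effect.

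**3. Precision of that yardstick.** The pilot SD is about 30/1.2 = 25. With 22 epochs treated as independent, SE = 25/√22 = 5.33, and the 95% interval is about -3.2 to +19.0, which includes 0.

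**4. Effect of the imputed value.** With missing fraction f in the active arm, observed active mean A and imputed value v, the estimate is (1 − f)·A + f·v − P. At the design effect A = 7.93 − 20 = −12.07. For example, zeros at f = 0.375 give 0.625 × (−12.07) + 0 − 7.93 = −15.47.

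| True effect, f | MAR | v = 0 | v = placebo mean | v = +44 |
|---|---|---|---|---|
| −20, 37.5% | −20.0 | −15.5 | −12.5 | +1.0 |
| −20, 20% | −20.0 | −17.6 | −16.0 | −8.8 |
| 0, 37.5% | 0 | −3.0 | 0 | +13.5 |
| 0, 20% | 0 | −1.6 | 0 | +7.2 |

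**5. Chance of passing.** Simulation at −20 and 37.5% missing (20,000 runs, Welch test on patient means, 25 of 40 observed per arm, placebo missing under MAR) gives significance in favour of the drug in about 0.90 of trials under MAR and 0.85 with zeros. The figure is 0.62 to 0.65 with placebo-based values (drawn with noise, or constant), and about 0 with +44%. The zero, constant-placebo and +44% figures use constant imputation, which the plan does not specify.

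**6. Size needed for significance.** With 25 observed per arm, SE = 21.2 × √(2/25) = 6.0, so significance needs about 2.01 × 6.0 = 12.1 points.

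**7. Tipping-point shift.** Adding a shift d to the MAR-imputed active values gives −20 + 0.375·d. Holding the SE at 6.0, significance goes at about d = (20 − 12.1)/0.375 = 21. At d = 44 the estimate is −20 + 16.5 = −3.5. A 44-point shift is not the same as assigning +44%, which here would need 44 + 12.07 = 56.07 points.

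**The case against.** A reader might infer that the scenario favours the drug, moving a result toward benefit. The documents do not support that as a general claim. The scenario is a check on results that are already significant. By step 6, a significant benefit with placebo near +7.93 means an active mean of about −4.1 or lower (7.93 − 12.1 = −4.2 with rounded inputs), so imputing 0 pulls the estimate toward the null relative to MAR. Zeros are kinder than MAR only if the active mean is above zero, which at that placebo mean requires an effect below 7.93 points. Run as a stand-alone test with no true effect and 37.5% missing, constant zeros would reject in the drug's favour about 8.1% of the time against a nominal 2.5%. The plan uses the scenario as added support, however, so the primary type I error is not raised. This objection stands.

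Other points also carry weight:

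- The term is undefined. It could mean no better than the untreated course, about +7.93%, and then the gap to the pilot mean disappears. That reading would match the reference-based rule proposed below, but the plan does not state it, and it would still not be a worst case.
- The scenario is an example beside a tipping-point analysis that could cover harsher values. With no range stated, nothing ensures that it will.
- The +7.93% is imprecise, and the +44% comes from previously stable lesions, not the trial population.
- The tipping-point sentence already mentions departure from MAR. Only the verb is wrong: observed data cannot verify MAR.
- Assigning +44% to every missing active-arm epoch is nearly unpassable. Section 9.3.2 projects missingness mainly from imaging (up to 10%) and follow-up (10%), and patients who bleed remain in scheduled imaging. This argues against +44% as a single pass/fail test, not against showing it.

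**Conclusion.** The concern holds in a limited form. Read as 0% change, the only named worst case is milder than the pilot's untreated mean and well short of what bleeding or growing lesions showed, so surviving it would overstate robustness. At the design effect with 37.5% missing, zeros cost the estimate 4.5 points (−20 to −15.5), against 7.5 points for the placebo mean. At 20% missing the costs are 2.4 and 4.0 points. The choice of value can decide whether robustness is claimed.

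This rests on reading the undefined term as zero, a placebo mean near +7.93%, and the plan's ceiling for missing data; less missingness shrinks the differences in proportion. The wording should be changed before unblinding. It does not affect the validity of the primary test, and it is not evidence that the sensitivity plan is tilted toward the drug.

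**What to change.** In the missing-data subsection of Section 9.5:

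- Replace the example with reference-based imputation: missing active-arm epochs are drawn from the placebo-arm distribution, and missing placebo epochs are imputed under MAR.
- Preset the active-arm tipping-point shift from 0 to +44 points, state that it is added to the MAR-imputed values, and report the shift at which significance is lost. Treat +44 as the extreme end, not a pass mark. On the design assumptions the tipping point is near 21 points, so this range would contain it.
- Describe the tipping-point analysis as assessing sensitivity to departures from MAR, and drop the claim that it verifies MAR.

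The cost is a few sentences and one or two more sensitivity runs, with no change to design or sample size. The downside is a stricter check: at the design effect with 37.5% missing, the simulated chance of staying significant falls from about 0.85 with zeros to 0.62-0.65 with placebo-based values.
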